8.2 Discontinuation From the Study

Withdrawal of consent for a study means that the subject does not wish to receive further protocol-required therapies or procedures, and the subject does not wish to or is unable to continue further study participation. Subject data up to withdrawal of consent will be included in the analysis of the study, and where permitted, **publicly** available data can be included after withdrawal of consent. The investigator is to discuss with the subject appropriate procedures for withdrawal from the study, and must document the subject's decision to withdraw in the subject's medical records.

If a subject withdraws from the study, he/she may request destruction of any samples taken and not tested, and the investigator must notify Amgen accordingly (see [Section 12.6](#) for further details). Refer to the Schedule of Activities ([Table 2-1](#)) for data to be collected at the time of study discontinuation and follow-up and for any further evaluations that need to be completed.

8.2.1 Reasons for Removal From Washout, Run-in or Invasive Procedures

Not applicable.

8.2.2 Reasons for Removal From Study

Reasons for removal of a subject from the study after enrollment/randomization are:

- Decision by sponsor
- Withdrawal of consent from study
- Death
- Lost to follow-up

8.3 Lost to Follow-up

A subject will be considered lost to follow-up if he or she repeatedly fails to return for scheduled visits and is unable to be contacted by the study site.

The following actions must be taken if a subject fails to return to the clinic for a required study visit:

- The site must attempt to contact the subject and reschedule the missed visit as soon as possible and counsel the subject on the importance of maintaining the assigned visit schedule and ascertain whether or not the subject wishes to and/or is able to continue in the study.
- In cases in which the subject is deemed lost to follow-up, the investigator or designee must make every effort to regain contact with the subject (where possible, 3 telephone calls and, if necessary, a certified letter to the subject's last known mailing address or local equivalent methods). These contact attempts are to be documented in the subject's medical record.
- If the subject continues to be unreachable, he/she will be considered to have withdrawn from the study with a primary reason of lost to follow-up.
- For subjects who are lost to follow-up, the investigator can search publicly available records (where permitted) to ascertain survival status. This ensures that the data set(s) produced as an outcome of the study is/are as comprehensive as possible.

9. Study Assessments and Procedures

Study procedures and their time points are summarized in the Schedule of Activities (see [Table 2-1](#)).

As protocol waivers or exemptions are not allowed if an enrolled subject is subsequently determined to be ineligible for the study, this must be discussed with the sponsor immediately upon occurrence or awareness to determine if the subject is to continue or discontinue study treatment.

Adherence to the study design requirements, including those specified in the Schedule of Activities, is essential and required for study conduct.

9.1 General Study Periods

9.1.1 Screening, Enrollment and/or Randomization

Informed consent must be obtained before completing any screening procedure. After the subject has signed the informed consent form, the site will register the subject in the IRT and screen the subject in order to assess eligibility for participation.

9.1.1.1 Screening Period

The screening period is up to 7 weeks, which consists of an up to 3-week initial screening period and a 4-week baseline period.

All screening evaluations must be completed and reviewed to confirm that potential subjects meet all eligibility criteria. The investigator will maintain a screening log to record details of all subjects screened and to confirm eligibility or record reasons for screening failure, as applicable.

If a subject has not met all eligibility criteria during the screening period, the subject will be registered as a screen fail. Screen fail subjects may be eligible for rescreening 1 time **if the condition that led to screen failure is expected to be transient.**

Rescreen subjects must first be registered as screen failures in IRT and subsequently registered as rescreens. Once the subject is registered as rescreened, a new **up to 7-week** screening period will begin. Subjects will retain the same subject identification number assigned at the original screening. If the rescreening period begins more than **60** days after the original signing of the informed consent form, all screening procedures, including informed consent, must be repeated.

9.1.1.2 Baseline Period

The 4-week baseline period starts when the subject has met all Part 1 eligibility criteria (refer to [Section 6.1](#) and [Section 6.2](#)) and enters the baseline period and ends when the subject **is randomized or** does not complete baseline or does not meet all Part 2 eligibility criteria (refer to [Section 6.3](#) and [Section 6.4](#)) **and is screen failed.**

The total duration of the baseline period must be at least 29 days and no more than 35 days. Refer to [Sections 9.2.2.1](#) and [9.2.2.3](#) for information on the BDI-II and eligibility calculation, which are to be completed at the end of the baseline period using the eDiary.

9.1.1.3 Randomization

Upon completion of the baseline period, subjects found to meet eligibility requirements will undergo randomization in **IRT** and be assigned a study treatment in a blinded manner.

9.1.2 Treatment Period

Visits will occur per the Schedule of Activities ([Table 2-1](#)). The date of the first dose of IP is defined as day 1. All subsequent doses and study visits will be scheduled based on the day 1 date. On-study visits may be completed \pm 3 days of the scheduled visit. Administration of IP is to be administered once every 4 weeks during each visit that it is required.

9.1.3 Early Termination

Upon permanent discontinuation from the study for any reason other than study completion or withdrawal of consent, an ET visit will be performed approximately 28 days after the last dose of investigational product.

Subjects who early terminate the study before week 24 should complete the week 24/ET assessments ([Table 2-1](#)).

Subjects who early terminate the study after week 24 and before week 52 should complete the week 52/EOS assessments ([Table 2-2](#)).

9.1.4 End of Study

Subjects who reach week 52 will end the study and complete all week 52/EOS assessments, according to [Table 2-2](#).

9.2 Description of General Study Assessments and Procedures

The sections below provide a description of the individual study procedures for required time points.

9.2.1 General Assessments

9.2.1.1 Informed Consent

All subjects must sign and personally date the IRB/IEC approved informed consent before any study-specific procedures are performed.

9.2.1.2 Demographics

Demographic data collection including sex, age, race, and ethnicity will be collected in order to study their possible association with subject safety and treatment effectiveness.

Additionally, demographic data will be used to study the impact on biomarker variability of the investigational product.

9.2.1.3 Medical History

The Investigator or designee will collect a complete medical (including targeted cardiovascular), psychiatric, and surgical history that started within 120 days prior to medical history assessment at screening. Medical history will include information on the subject's concurrent medical conditions. Record all findings on the medical history CRF. In addition to the medical history above, migraine history must date back to the original diagnosis. The current severity will be collected for each condition that has not resolved.

Targeted medical history is to be recorded in the neurologic medical history CRF, cardiovascular medical history CRF, **cardiac risk factors CRF**, and headache and migraine frequency medical history CRF.

9.2.1.4 Physical Examination

Physical examination will be performed as per standard of care. Physical examination findings should be recorded on the appropriate CRF (eg, medical history, event).

9.2.1.5 Physical Measurements

Height (in centimeters) should be measured without shoes. Weight (in kilograms) should be measured without shoes.

9.2.1.6 Performance Status

Not applicable.

9.2.2 Efficacy Assessments

9.2.2.1 Clinical Outcome Assessments and Electronic Diaries (eDiaries)

The COAs will be collected by subjects using a handheld eDiary at various frequencies. The eDiary will collect the following COAs daily at home starting in the baseline period and throughout the DBTP, and then again daily starting from week 40 **visit** through the week 52/EOS visit of the OLTP:

- Date and time of start of headache (ie, migraine or nonmigraine headache)
- Date and time of end of each headache
- Worst pain severity per headache day
- Pain features (eg, 1-sided, throbbing, worsens, with exercise/physical activity)
- Other migraine symptoms (eg, aura, nausea, vomiting, photophobia, phonophobia)

Approved

- Use of acute medications **to treat headaches or migraine symptoms** (medication name [from pre-entered list] date and time of dosing, number of times taken of each date, number of units taken)

Study center staff will assign and provide an eDiary to the subject at the week -4 visit (after confirming the subject's part 1 eligibility prior to baseline period entry). The study center staff will train the subject on how to use the eDiary (eg, turning on/off, charging, navigating screens, transmitting data, contacting the help desk for technical assistance) and complete the questions. The subject will be instructed to interact with the eDiary every day and to bring the eDiary to every study visit. **During the baseline period after at least 28 full calendar days have passed (inclusive of the day the subject was set-up on the eDiary device), the subject will return for their end of baseline period visit/ day 1 visit.** At the day 1 visit, the investigator will use the subject's eDiary to review all data entered during the baseline period and confirm the relevant inclusion and exclusion criteria. **During this visit, site staff will be able to activate the baseline period BDI-II on the subject's eDiary device, as well as perform the eligibility calculation.**

For randomized subjects, all Day 1 study assessments, including eDiary questionnaires, should be completed prior to subject's first dose of investigational product. For subsequent study visits, the order of completing study assessments will be at the investigator's discretion.

The subject's eDiary will also be used for the completion of the following patient-reported outcome measures:

- MPFID
- HIT-6
- MFIQ
- MIDAS questionnaire
- Sleep questionnaire
- Allodynia symptoms checklist 12 items (ASC-12) questionnaire
- BDI-II
- GAD-7
- PGIC

Approved

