^a The baseline period ends when either a subject is screen failed or randomized into the study. Randomization occurs at the Day 1 visit which must occur between 29 to 35 days after baseline entry (inclusive of the first day that eDiary device is assigned to subject).

^b On Day 1, all study assessments should be completed prior to subject's first dose of investigational product.

^c A subject who discontinues the study during the DBTP will complete the assessments of the week 24/ET visit approximately 28 (+3) days after the last dose of investigational product.

^d Including pre-filled syringe in DBTP and autoinjector during OLTP.

^e All clinical laboratory testing at screening (except pregnancy testing) will be performed at a central laboratory.

^f Additional on-treatment local laboratory pregnancy testing may be performed at the investigator's discretion if there is suspicion that a female subject is pregnant or per local laws and regulations.

^g For subjects who provided informed consent for the pharmacogenetic studies, DNA will be obtained from residual cells from the biomarker blood sample. Therefore, additional sampling is not required.

^h The BDI-II will be collected via paper CRF during screening and eDiary thereafter.

ⁱ The Baseline Period BDI-II will be completed at the end of the Baseline Period using the eDiary, after at least 28 days of data has been entered in the eDiary.

Approved

Product: Erenumab
Protocol Number: 20170703
Date: 27 May 2020

J The baseline HRU questionnaire will have a 24-week recall of prior utilization. The HRU questionnaire assessed at the ET visit before week 24 should only include HRU recalled since the previous assessment to avoid collecting duplicate information. For example, the 24-week HRU questionnaire assessed at week 20 as the ET visit should only include HRU recalled since the previous assessment at day 1 (ie, 20-week recall).

Approved

Table 2-2. Schedule of Activities - Study Visits Through Open-label Treatment Period

	Treatment Period								
	Open-label Treatment Period (28 Weeks)								
PROCEDURE	Wk 24 (OLTP Entry Visit)	Wk 28	Wk 32	Wk 36	Wk 40	Wk 44	Wk48	Wk 52/ EOS ^a	Notes
GENERAL AND SAFETY ASSESSMENTS									
Clinic Visit	X	X			X			X	
Telephone Contact			X	X		X	X		
IRT call ^b	X	X			X			X	
Physical examination	X				X			X	
Vital signs	X				X			X	BP, HR, RR, and temperature
Adverse events	X	X	X	X	X	X	X	X	
Serious adverse events	X	X	X	X	X	X	X	X	
Adverse device effects ^c	X	X	X	X	X	X	X	X	

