^b All subjects will be enrolled via **IRT** in the OLTP to maintain the initial treatment blinding in DBTP. Subjects who received active treatment during the DBTP will remain on the same dose. Subjects who received placebo will receive either 70 mg or 140 mg in a 1:1 ratio.

^c Including pre-filled syringe in DBTP and autoinjector during OLTP.

^d Additional on-treatment local laboratory pregnancy testing may be performed at the investigator's discretion if there is suspicion that a female subject is pregnant or per local laws and regulations.

^e Study drug supply ceases at week 48.

Approved

Table 2-3. Schedule of Activities – Optional Interview-based Substudy (Selected US Sites Only)

PROCEDURE			Treatment Period							Notes
	Screening Period	Baseline Period	Double-blind Treatment Period (24 Weeks)							
	(up to 3 weeks before Baseline)	(4 weeks before Day 1)	Day 1 (post-rand)	Wk 4	Wk 8	Wk 12	Wk 16	Wk 20	Wk 24/ ET	
INTERVIEW-BASED SUBSTUDY										
Substudy informed consent			X ^a							
Substudy Eligibility Requirements			X							
Interview ^b			X ^c						X ^d	

DBTP = double-blind treatment period; ET = early termination; US = United States.

^a The Substudy subject informed consent can also be obtained at the same time as the main study informed consent during Screening instead of after randomization.

^b The first interview (Interview 1) will be conducted within the first week after randomization, the second interview (Interview 2) will be conducted within 1 week after the subject's last visit during the DBTP.

^c The entry interview will be conducted within 7 days from first investigational product dose.

^d The exit interview will be conducted in close proximity with the week 24 or early termination visits (within 7 days prior to week 24 visit or within approximately 14 days post early termination visit. If possible within 7 days post early termination will be targeted).

Approved

3. Introduction

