5.3 Study Points of Reference

Baseline Assessment

Baseline assessment for the endpoint of the interest is defined as the last non-missing measurement taken or the monthly interval assessed (for endpoints derived from daily eDiary collection) before the first dose of investigational product. In cases where baseline measurements are taken on the same day as IP, it will be assumed that these measurements are taken prior to IP being administered. For subjects who are randomized but not dosed after the randomization, the baseline of the study is defined as the last non-missing measurement prior to or on the date of randomization.

For measurements with multiple individual items, such as MFIQ and ARMR, all individual items from the same set of measurement will be used for analysis.

Pre-OLTP Baseline

Pre-OLTP baseline is defined as the last non-missing measurement for the endpoint of interest taken before the first dose of OLTP IP. In cases where the

measurements are taken on the same day as the first dose of OLTP IP, it will be assumed that these measurements are taken prior to IP being administered. For endpoints derived based on daily eDiary data, the pre-OLTP baseline is the last non-missing monthly measurement before the first dose of OLTP IP.

Study Day 1

Study day 1 is defined as the first IP dose date **regardless on or after randomization date**. For subjects who are randomized but **never received any dose**, the study day 1 is defined as the date of randomization.

Study Day

Study Day is defined as the number of days from study day 1.

Before Study Day 1:

$$\text{Study Day} = (\text{Date of Interest} - \text{Date of Study Day 1})$$

On or after Study Day 1:

$$\text{Study Day} = (\text{Date of Interest} - \text{Date of Study Day 1}) + 1$$

Therefore, the day prior to Study Day 1 is -1.

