5.4.3 Analysis Visits for Endpoints Based on Monthly Collection

Since the actual visit for a subject may not exactly coincide with their targeted visit date, the actual visit date is mapped to the analysis visit as in [Table 5-2](#) to [Table 5-7](#).

By-visit data collected on or before the first OLTP dose date belong to DBTP. Data collected after the first OLTP dose date, not including the safety follow-up visit, belong to OLTP. Any data occurred after EOS date will not be included in the analysis except antibody data.

For by-visit summaries, if more than one visit with non-missing measurement (including the unscheduled visits, ie, CPEVENT = 'UNSCHED') fall within the same visit window, the following rules will be applied according to the order described below for selecting one visit per visit window for summary:

1. Scheduled visit will be used regardless of the distance from the target day. Unscheduled visit will only be used when there is no measurement from scheduled visit in the visit window.
2. The visit closest to the target day will be considered for analysis.
3. If two assessment dates are equidistant from the target date, the latter visit will be considered for analysis.

Table 5-2. HIT-6 and MFIQ Analysis Visit Windows

Study Period	Analysis Visit	Target Day	Visit Window (Study Day)
Double-blind Treatment Period	Day 1 (Baseline)	1	Last measurement prior or on Day 1
	Week 4 (Month 1)	29	16 to 43
	Week 8 (Month 2)	57	44 to 71
	Week 12 (Month 3)	85	72 to 99
	Week 16 (Month 4)	113	100 to 127
	Week 20 (Month 5)	141	128 to 155
	Week 24 (Month 6)	169	156 to Week 24 dose date, if available, else to 183
Open-label Treatment Period	Week 52 (Month 13)	365	352 to 379

Table 5-3. MIDAS Analysis Visit Windows

Study Period	Analysis Visit	Target Day	Visit Window (Study Day)
Double-blind Treatment Period	Day 1 (Baseline)	1	Last measurement ≤ Day 1
	Week 12 (Month 3)	85	72 to 99
	Week 24 (Month 6)	169	156 to Week 24 dose date, if available, else to 183
Open-label Treatment Period	Week 52 (Month 13)	365	352 to 379

Table 5-4. ASC-12/GAD-7/BDI-II/Sleep Questionnaire Analysis Visit Windows

Study Period	Analysis Visit	Target Day	Visit Window (Study Day)
Double-blind Treatment Period	Day 1 (Baseline)	1	Last measurement ≤ Day 1
	Week 12 (Month 3)	85	72 to 99
	Week 24 (Month 6)	169	156 to Week 24 dose date, if available, else to 183

Table 5-5. PGIC Analysis Visit Windows

Study Period	Analysis Visit	Target Day	Visit Window (Study Day)

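### Nothing requires the week-24 double-blind questionnaires to be completed before the first open-label dose, yet the SAP analyses same-day ratings as double-blind data

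*Protocol*

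**What the plan says.** Protocol section 9.2.2.1 sets a firm order for Day 1: "all Day 1 study assessments, including eDiary questionnaires, should be completed prior to subject's first dose of investigational product". Its next sentence says that, at later visits, "the order of completing study assessments will be at the investigator's discretion". Table 2-1 footnote b is also confined to the first visit: "On Day 1, all study assessments should be completed prior to subject's first dose of investigational product". Neither place mentions week 24.

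Table 2-1 schedules vital signs, HIT-6, MFIQ, ASC-12, MIDAS, BDI-II, GAD-7, the sleep questionnaire and PGIC at week 24/ET. Table 2-2 makes week 24 the OLTP entry visit, with an IRT call, autoinjector training and self-injection of the first open-label dose in clinic.

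SAP section 5.4.1 runs the DBTP, for efficacy assessments at scheduled visits and for vital signs, up to and including the first open-label dose date. Section 5.4.3 repeats this: "By-visit data collected on or before the first OLTP dose date belong to DBTP". The week-24 windows in Tables 5-2 to 5-5 and 5-7 extend to the week-24 dose date where there is one. For the pre-OLTP baseline, section 5.3 adds that where measurements fall on "the same day as the first dose of OLTP IP, it will be assumed that these measurements are taken prior to IP being administered".

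**The concern.** From week 4 to week 20 the order within a visit matters little, because the dose given is itself blinded. Week 24 differs. Once allocation, training and injection have taken place, the subject knows that active erenumab has been given. A questionnaire handed over after that point is no longer answered under the conditions of the placebo-controlled period.

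The SAP makes the same same-day assumption for the study baseline, but there the Day 1 rule in the protocol backs it. At week 24 no such rule exists, and the SAP has no step that would flag a rating made after the open-label dose. At stake is whether some week-24 patient-reported outcomes, including one tested under the EU hierarchy, are really blinded ratings.

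**Working it through.** The plan gives no figure on this point to reproduce. The stated power concerns the primary endpoint, which is not exposed. The check is mainly a comparison of texts.

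**1. Is there an order rule at week 24?** Day 1 has one, in section 9.2.2.1 and in footnote b. For later visits the only statement is the discretion sentence. Table 7-1 has placebo subjects allocated by IRT once the DBTP is complete, and SAP section 5.5 defines completion by the week-24 assessment. Together these suggest assessments first and allocation second. Neither says that the questionnaires must be finished before the injection.

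**2. How does the SAP classify data dated on the first open-label dose day?**

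| Data | Period assigned | Source |
|---|---|---|
| Scheduled-visit efficacy, vital signs | DBTP | SAP 5.4.1, 5.4.3 |
| Adverse events, concomitant medications | OLTP | SAP 5.4.1 |
| Daily diary, month 6 | Stops the day before the dose | SAP Table 5-1 |

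**3. Which endpoints are exposed?**

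| Endpoint | Status | Share resting on week 24 |
|---|---|---|
| HIT-6 (EU) | Alpha-controlled, last two EU steps | 1 of 3 visits (weeks 16, 20, 24) |
| PGIC | Exploratory | The only rating |
| MFIQ, MIDAS, ASC-12, GAD-7, BDI-II, sleep | Exploratory | The week-24 value |
| Primary, sustained remission, AHMD, MPFID | Primary and secondary | None (daily diary) |

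Only subjects dosed at the week-24 visit can be affected. Those who terminate early or decline the OLTP cannot. The week-24 values of HIT-6, MFIQ, MIDAS and vital signs also serve as the pre-OLTP baseline, but OLTP analyses are descriptive (SAP 9.5.4, 9.6.1).

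**4. What scale could a HIT-6 effect have?** Let f be the share of an arm rated after dosing and s the mean shift in their week-24 score. The documents give neither, so both are assumptions. With equal weight on the three visits, the arm mean moves by f × s / 3:

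- f = 1 and s = 1, 2, 3 or 5 points: 0.33, 0.67, 1.00 or 1.67 points
- f = 0.5 and s = 2: 0.5 × 2 / 3 = 0.33 points
- f = 0: no movement

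The treatment comparison moves by (f_E × s_E − f_P × s_P) / 3, where E is an erenumab arm and P is placebo. Equal shares and shifts give zero, and the sign can go either way.

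**5. What would the subject learn about the original arm?** Subjects on active drug keep their dose, and placebo subjects are split 1:1. Assume that the open-label dose is visible and that equal proportions of each arm enter the OLTP. The chance of having been on the dose now received is then (1/3) / (1/3 + 1/3 × 1/2) = 2/3, up from 1/3. The chance of having been on placebo stays at 1/3. One arm is ruled out, but the odds of active versus placebo do not change.

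**The case against.** The discretion sentence most naturally concerns the order among assessments. A reader might infer that it permits injecting first and rating afterwards; the documents do not say that. The protocol is silent on the point, and the text on DBTP completion leans the other way. This stands, but an implied sequence is weaker than the explicit rule written for Day 1.

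The bias mechanism is also modest. Every OLTP entrant receives erenumab, and the open-label option is part of the design, so a subject may expect active drug before opening any week-24 questionnaire. Subjects stay blinded to their original assignment (protocol 5.1). Much of the content is retrospective: the last three HIT-6 items look back 4 weeks, MIDAS and the sleep questionnaire 3 months, and PGIC covers change since treatment started. This limits the likely effect without removing it. The first three HIT-6 items have no recall period, and PGIC is a global judgement.

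Finally, no passage says that questionnaire completion times are captured. Section 9.2.2.1 lists times for headaches and medication intake, and Table 7-1 records the dose start time. That stands and makes the SAP part of the remedy conditional.

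**Conclusion.** The gap is real and worth closing, as a cheap improvement. The plan allows week-24 patient-reported ratings to be made after the open-label dose and would analyse them as double-blind. The alpha-controlled exposure is confined to HIT-6 in the EU, at one of its three visits; the other exposed scales are exploratory.

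Four stronger readings are not supported:

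- That the primary result is compromised. Its diary interval closes the day before the dose.
- That the SAP assigns everything dated on that day to the DBTP. Adverse events and concomitant medications go to the OLTP.
- That the bias favours erenumab. No direction between arms can be derived from the documents.
- That the point shifts above are estimates. They only convert assumed inputs.

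How often sites would dose before rating is not documented.

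A separate inconsistency concerns the exit interview in the optional substudy (up to 30 subjects). Table 2-3 footnote b says that "the second interview (Interview 2) will be conducted within 1 week after the subject's last visit during the DBTP", and section 9.2.12 likewise allows up to a week after that visit. Footnote d says "within 7 days prior to week 24 visit or within approximately 14 days post early termination visit". Appendix 8 is not uniform: its Substudy Design paragraph gives 7 days around week 24 without a direction, while its exclusion criteria and procedures say before the visit. A reader might infer that Appendix 8 consistently requires the earlier timing; it does not.

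**What to change.** - **Protocol.** Extend Table 2-1 footnote b and section 9.2.2.1 so that all week-24 double-blind assessments and questionnaires are completed before OLTP allocation, autoinjector training and the first open-label dose. This takes one sentence. Its cost is slightly less scheduling freedom for sites at that visit.
- **SAP.** If questionnaire completion times are available, add a sensitivity analysis that excludes week-24 ratings completed after the open-label dose start time, and report how many there were. If week-24 visits have already taken place, this check alone would still show whether the assumption in section 5.3 held. If the times are not captured, state the assumption as a limitation.
- **Substudy.** Reconcile the exit-interview timing across Table 2-3 footnotes b and d, section 9.2.12 and the passages in Appendix 8.
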